5.2 Use of co-intervention

The use of oral co-medication is allowed, as in regular daily practice. The treating neurologist supervises any changes in medication. The main motivation for this approach is to stay close to regular daily practice routines for reason of generalizability.

Version 7: 23-10-2019 20 of 48

6. INVESTIGATIONAL PRODUCT

The medicinal product under investigation in this study is Duodopa, an intestinal gel containing levodopa and carbidopa, produced by Abbott pharmaceuticals. The information being referred to in the next section is derived from the Summary of Product Characteristics (SPC) of Duodopa, which is available in appendix 13.2 and D2 SPC Duodopa. The product will be used according to market authorization. The study does not contain any investigation of unauthorized use of Duodopa.

6.1 Name and description of investigational product(s)

For a description of Duodopa intestinal gel, see page 1-3, section 1 to 4.2 of the SPC (appendix 13.2).

6.2 Summary of findings from non-clinical studies

For a summary of findings from non-clinical studies on Duodopa intestinal gel, see page 15, section 5.3 of the SPC (appendix 13.2).

6.3 Summary of findings from clinical studies

Four RCTs [13, 17-19] and a number of lower quality studies evaluated CLI by comparison with best oral medical treatment. Overall, CLI showed improvements regarding PD motor symptoms (UPDRS motor examination), ON-phase time, and functional health. Two CLI RCT's also assessed patient-reported perceived quality of life with the PDQ-39, which improved in correlation with motor symptoms and functional health. [13, 18]

6.4 Summary of known and potential risks and benefits

For a summary of potential undesirable effects of Duodopa intestinal gel, we refer to page 3-11, section 4.3 to 4.9 of the SPC (appendix 13.2).

6.5 Description and justification of route of administration and dosage

For a description of the pharmacological properties both pharmacodynamics and pharmacokinetics see page 8 and 9, section 5.1 and 5.2 of the SPC (appendix 13.2).

6.6 Dosages, dosage modifications and method of administration

For a description of posology and the method of administration see page 2 to 3, section 4.2, of the SPC (appendix 13.2).

Version 7: 23-10-2019 21 of 48

The total dose/day of Duodopa is composed of three individually adjusted doses: the morning bolus dose, the continuous maintenance dose and extra bolus doses.

Morning dose: The morning bolus dose is administered by the pump to rapidly achieve the therapeutic dose level (within 10-30 minutes). The dose is based on the patient's previous morning intake of levodopa and the volume to fill the tubing. The total morning dose is usually 5-10 ml, corresponding to 100-200 mg levodopa. The total morning dose should not exceed 15 ml (300 mg levodopa).

Continuous maintenance dose: The maintenance dose is adjustable in steps of 2 mg/hour (0.1 ml/hour). The dose is calculated according to the patient's previous daily intake of levodopa. When supplementary medicines are discontinued the Duodopa dose should be adjusted. The continuous maintenance dose is adjusted individually. It should be kept within a range of 1-10 ml/hour (20-200 mg levodopa/hour) and is usually 2-6 ml/hour (40-120 mg levodopa/hour). In exceptional cases a higher dose may be needed.

Extra bolus doses: To be given as required if the patient becomes hypokinetic during the day. The extra dose has to be adjusted individually, normally 0.5-2.0 ml. In rare cases a higher dose may be needed. If the need for extra bolus doses exceeds 5 per day the maintenance dose should be increased.

After the initial dose setting, fine adjustments of the morning bolus dose, the maintenance dose and extra bolus doses should be carried out over a few weeks.

Version 7: 23-10-2019 22 of 48

7. METHODS

7.1 Study parameters/endpoints

7.1.1 Main study parameter/endpoint

Outcome parameters

The primary health economic outcomes of the randomized trial are the costs per unit on the PDQ-39 and the costs per QALY for the cost-effectiveness and cost-utility analyses respectively. The EQ-5D will be applied as the utility measure.

For a detailed motivation for outcome measures see appendix 13.3.

7.1.2 Secondary study parameters/endpoints

The main clinical outcome is quality of life (PDQ-39), Other secondary parameters are:

PD motor symptoms (Movement Disorder Society - Unified Parkinson's Disease Rating Scale (MDS-UPDRS), Clinical Dyskinesia Rating Scale (CDRS), 3-day motor symptom diary), non-motor symptoms such as autonomic functions and sleep (Non Motor Symptom Checklist, Rotterdam Symptom Checklist), neuropsychological and psychiatric assessment, possible cognitive decline on PD_CRS, Hoehn & Yahr stage, functional health status (ALDS), PD-medication, patient and physician preferences, Satisfaction with Life Scale, treatment satisfaction, adverse effects and complications, treatment failure, stopping treatment, starting with the alternative than initially started treatment, caregiver burden, (informal) care use and medical and non-medical care costs evaluated with the Institute for Medical Technology Assessment Productivity Cost Questionnaire (iMCQ) and Institute for Medical Technology Assessment Productivity Cost Questionnaire (iPCQ).

7.1.3 Other study parameters

When possible, a few baseline values will be collected from all patients, if possible including those not willing to be included in the patient preference trial study (anonymously), such as age, sex, medication, age of onset of PD, duration of PD, comorbidities, preference for treatment and possible reasons not to participate in the study.

7.2 Randomisation, blinding and treatment allocation

The randomization procedure will be website-based, using random blocks and stratified by:

Version 7: 23-10-2019 23 of 48

level of experience of the including centre with DBS and CLI therapy (experienced DBS centres have treated at least 5 patients with DBS in the last two years and an experienced CLI centre has treated at least 5 patients with CLI each year in the last two years);

7.3 Study procedures

See also figure 1 and appendix 13.4 (assessment schedules). A patient can participate in the RCT after inclusion by the treating neurologist of a centre registered as a study site. Patients not willing to be randomized can participate in the patient prerefence trial in which only telephonic assessments will be executed either through 1. inclusion by the treating neurologist in a centre registered as a study site; 2. providing contact information of the patient to the study team (approved by the patient) by a neurologist not registered as a study site whereafter the patient will be additionally informed by the team and informe consent will be signed; 3. direct registration by the patient with the INVEST study team, whereafter, if approved by the patient, the treating neurologist will be asked whether the patients fulfills the in- and exclusion criteria This procedure is described in 9.2, Recruitment and consent.

RCT

If the patient agrees to be randomized, a trial nurse will make an appointment for the first visit. There are eight specified assessment visits: at baseline and 1 week, 3 months, 6 months, 9 months, 12 months, 24 months and 36 months after start of the study treatment (visits 1, 2, 3, 4, 5,6, 7 and 8). The last two assessments were added after the start of the trial. Additional follow-up might provide very relevant data on long term costs, side-effect and cross-over. Regarding visits 2, 3, 4, and 5, the visits for standard care in both CLI and DBS are extended with the questionnaires for the study or the patients will be interviewed. For the assessment schedule please see appendix 13.4, document F1 "Vragenlijsten" will give an outline of all used scales and questionnaires.

At baseline (visit 1), age, sex, educational level, medication, age at onset of PD, duration of PD, Hoehn and Yahr stage, and comorbidities will be recorded. In addition, he or she will have an electrocardiogram (EKG), CT/MRI-scan of the head, and fasting blood analysis for sodium, potassium, creatinine, glucose, prothrombin time (PT), activated partial thromboplastin time (aPTT), leukocytes, erythrocytes, platelets. Vitamin B6, B12 and folic acid will be analysed.

Former participation in medical research and reason(s) to participate in this study will be evaluated. Patients will keep a motor symptom diary (3 days; including ON/ OFF phases,

Version 7: 23-10-2019 24 of 48

dyskinesias, and sleep states). The patients will have an assessment containing the MDS-UPDRS and the AMC Linear Disability Score (ALDS) in standardized OFF and ON phases. The OFF phase is defined as the condition of the patient after withholding PD medication for 12 h and being awake for at least 1 h. The ON phase is the condition 1 h after a supra-threshold levodopa dose. The supra-threshold levodopa dose is based on the patient's usual first morning dose of PD drugs. To calculate the supra-threshold levodopa dose, different drugs will be pooled in Levodopa Equivalent Doses. The standardized OFF and ON phases examination will be videotaped. In the ON phase the patient will also undergo documentation of the Non Motor Symptom Checklist, Parkinson's Disease Impulsive-Compulsive Disorders Questionnaire, Hoehn and Yahr stage, ALDS, Rotterdam Symptom Checklist, Clinical Diskinesias Rating Scale (CDRS), patient-reported perceived quality of life (PDQ-39), EuroQol-5D (EQ-5D), iMTA Medical Consumption Questionnaire (iMCQ), iMTA Productivity Cost Questionnaire (iPCQ), use of (informal) care, apathy assessed by researcher and caregiver, caregiver burden and preference for treatment. The trial nurse will also administer the Mini-International Neuropsychiatric Interview (MINI) [20] and the Columbia Suicide Severity Rating Scale to screen psychiatric morbidity. The patients will undergo a neuropsychological examination including the Mattis Dementia Rating Scale and the Parkinson's Disease Cognitive Rating Scale (PD-CRS) and Patient-reported outcome tool for advanced Parkinson's disease (PROAPD) and a standardized psychiatric assessment.

After baseline screening, patients eligibility for both treatments will be discussed with the appropriate disciplines (neurology, neuropsychology, neurosurgery, and gastroenterology) in the treating centre, or the centre that will provide the treatment. If any possible contraindications for one of the treatments is found, the patient will be excluded from the study. Possible contra-indications are a non-dopamine responsive tremor as main complaint or if the effect of dopaminergic medication on motor symptoms is too small. Subsequently, the patient is randomized using a web-based application. Dependent on the result of randomization, the patient will be treated in the own hospital or he or she will be referred to one of the cooperating DBS centres. Within 3 months after the baseline assessment the study-treatment — DBS or CLI — will be started. The treatment will be performed as described in section 5.1

At visits 2, 3, 4, 5, 6, 7 and 8 patients will undergo documentation of PD-medication, adverse events (through a standardized questionnaire), treatment failure and cross-over. The iMCQ, iPCQ, use of (informal) care and caregiver burden are assessed at visit 3, 4, 5, 6, 7 and 8. At visits 5, 6, 7 and 8 we will record the PDQ-39. At visit 6, 7 and 8 the patients

Version 7: 23-10-2019 25 of 48

will keep a motor symptom diary (3 days; including ON/ OFF phases, dyskinesias, and sleep states) and the Non Motor Symptom Checklist, ALDS and patient satisfaction with the treatment. At visit 6 we will record the MDS-UPDRS, the CDRS and blood analysis as described above will be repeated. Also, patients will undergo a short neuropsychological examination and standardized psychiatric assessment at visit 6 and 8. The first year of follow-up, a margin of one month is deemed acceptable in planning a visit, for the second and third year of follow-up, the visits will be completed within two months of the defined follow-up date.

Patient preference trial

Patients that are not willing to participate in the RCT, but do take part in the ancillary patient preference observational study, will have a baseline visit with a limited set of evaluations. At the baseline visit, age, sex, medication, age at onset of PD, duration of PD, Hoehn and Yahr stage, and comorbidities will be recorded. The patients will have an assessment of the patient-reported perceived quality of life (PDQ-39) and will fill in a questionnaire on preference for treatment and expectations (PROADP). Follow-up visits are planned at 9 months, 12 months, 24 months and 36 months after the study treatment. In these visits, the PDQ-39 and patient satisfaction with the treatment will be assessed (PROADP), complications and adverse events will be evaluated using a questionnaire and the medical charts will be reviewed for complications and adverse events. If necessary, based on complications and adverse events questionnaire, the medical information from other hospitals will be requested and reviewed. The first year of follow-up, a margin of one month is deemed acceptable in planning a visit, for the second and third year of follow-up, the visits will be completed within two months of the defined follow-up date.

Furthermore, during the study current preferences regarding treatment of advanced PD amongst treating physicians will be evaluated.

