7.5 Follow-up of subjects withdrawn from treatment

The analysis of the study will be based on the intention-to-treat principle. In case a patient stops the study-treatment (CLI or DBS), the authors will strive to continue the follow-up assessments. In other words, a patient that stops the study-treatment is not considered to be a dropout. We will record the number of patients that stop the assigned study-treatment, the number of patients that crossover to the "other" study-treatment, and the number of patients that eventually need the "other" treatment in addition to the initially assigned study-treatment. Hence, these protocol violations are considered to be important secondary outcomes parameters of the study.

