8.7 Primary study parameter(s)

Statistical analyses will be based on the intention-to-treat principle. Baseline assessments and outcome parameters will be summarized using simple descriptive statistics. The main health economic analyses are a cost-effectiveness analysis based on costs and quality of life measured with the PDQ-39 and a cost-utility analysis, using the EQ-5D utility measure. (see also appendix 13.5 "Cost effectiveness analysis" and 13.6 "Patient Outcome Analysis").

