8.8 Secondary study parameter(s)

RCT

The main clinical analysis of the study consists of a comparison between the trial treatment groups (DBS versus CLI) of the primary clinical outcome (PDQ-39) 12 months after the start of the study treatment. First, the follow-up difference between PDQ-39 scores will be analysed using a two-group t-test. Second, the PDQ-39 follow-up scores will be further investigated using multiple linear regression taking into account patients' PDQ-39 baseline values, the stratifying variables (experience of the including centre with DBS and CLI; response to Levodopa) and (if necessary) for clinically relevant baseline imbalances. Additionally, the repeated data structure will be investigated with a linear mixed model. The same analyses will be performed for the 24 and 36 month outcomes. With regard to the comparisons of the other secondary outcomes PD motor symptoms (MDS-UPDRS, CDRS, 3-day motor symptom diary), non-motor symptoms such as autonomic functions and sleep (Non Motor Symptom Checklist, Rotterdam Symptom Checklist), PD-medication, neuropsychological and psychiatric assessment, disability, functional health status (ALDS), patient and physician preferences, patient satisfaction, adverse effects and complications, treatment failure, stopping treatment, starting with the alternative than initially started treatment, caregiver burden and medical and non-medical care costs (iMCQ, iPCQ) we will use the appropriate parametric and non-parametric statistics. In all analyses, statistical uncertainties will be expressed in 95% confidence intervals.

Patient preference trial

As mentioned before a patient preference observational study will be conducted to asses external validity of the randomized controlled trial results. The primary clinical outcome of the non-randomized group and randomized group will be compared using the two-group t-test and linear regression, whereas baseline characteristics will be compared with the

Version 7: 23-10-2019 32 of 48

two-group t-test and Chi-square test, when appropriate. Finally, the impact of the treatment on the PDQ-39 follow-up scores of the randomized and non-randomized group will be analysed using multiple linear regression, adjusting for relevant imbalanced baseline variables and randomized status (agreeing to randomization or not).

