Originally, an intention-to-treat analysis (ITT) was planned as the primary analysis. Nevertheless, during the study it was observed that after allocation, several patients immediately refused CLI treatment and either chose to be treated with DBS or quitted study participation. Analyzing these patients in an ITT could have introduced a significant bias, as their apparent preference for DBS made them not representative of a population that considered CLI a suitable treatment for advanced PD. Furthermore, for the patients for whom post-baseline data were not available, all these data would have had to be imputed, contributing to the risk of bias. A modified intention-to-treat (mITT) population was introduced as the primary analysis, because analysis in the ITT population including all randomized individuals was considered less valid.⁷ The mITT population included all randomized patients who received the allocated treatment and continued in the RCT after randomization. Additionally, in line with the proposed strategy for ITT analyses for trials with incomplete outcome data as proposed by White et al.,⁷ sensitivity analyses were performed to explore the robustness of the main analyses in the mITT population and included analyses in all randomized patients (the ITT population). Please see “Sensitivity analysis” for details on page 12.

While conducting the study, it was observed that comorbidities had a negative impact on completeness of the follow-up data. To assess for a possible bias towards a selective data collection of healthier patients, treating physicians of patients that had dropped out of the study were contacted to obtain additional information on the general health status and level of functioning of these patients. Please see also “Patient replacement and missing data” on page 10.

Study methods

Outcomes - randomized controlled trial

Primary outcomes

The main clinical outcome was the change from baseline to 12 months after initiation of treatment in PDQ-39 (score 0-100).⁸

The primary health economic outcomes are elaborated on page 19.

Secondary outcomes

- PD motor symptoms -- Movement Disorder Society’s Unified Parkinson’s Disease Rating Scale (MDS-UPDRS) part III in on-drug state (score range 0-132) ²;
- Motor experiences of daily living-- MDS-UPDRS part II in on-drug phase (score range 0-52) ²;
- Dyskinesia -- Clinical Dyskinesia Rating Scale (CDRS, score range 0-28) in on-drug state ⁹;

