In line with the proposed strategy for ITT analyses for trials with incomplete outcome data as proposed by White et al, analyses were performed in the ITT population, including the patients who had been excluded from the mITT population (*i.e.*, patients who immediately after randomization either had chosen not to accept the allocated treatment or had quitted participation in the study).⁷ For missing values for the main clinical outcome in the analyses in the ITT population, the approach for handling missing values as used for the mITT analyses as described in “Patient replacement and missing data” on page 10 was applied; first making use of the previously imputed values for the mITT population and additionally imputing missing values of the ITT-population based on the total population according to the conformity scenario and the most applicable worst case scenario chosen for the mITT analysis. In addition, a “best case” scenario was applied as for patients who immediately quitted study participation after randomization and for whom the main clinical outcome at 12 months was missing, a favorable outcome was possible. In this scenario, for patients who immediately quitted study participation after randomization, missing values for the 12-month PDQ-39 summary index score were imputed with the highest PDQ-39 in the treatment arm the patient had been allocated to. Other missing values were imputed according to the previously described conformity scenario.

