The primary health outcome in the cost-effectiveness analysis was the change in the PDQ-39 between baseline and 12 months after randomization. The change score showed the increase or decrease in number of difficulties across eight different dimensions of health (including mobility, activities of daily living, emotional well-being, and stigma) as experienced by patients in the preceding month. Dimension scores are coded on a scale of 0 (perfect health as assessed by the measure) to 100 (worst health as assessed by the measure). The change score was defined as the mean score on the eight scales at month 12 minus the mean score at baseline, in theory ranging from -100 to +100 with a score of 0 representing 'no change'.

The primary health outcome in the cost-utility analysis was the number of QALYs. Patient's health status was assessed with the EQ-5D-3L at baseline, one week, three months, six months, nine months, and 12 months post randomization. The EQ-5D contained five items: mobility, self-care, usual activities, pain/complaints, and mood (anxiety/depression).³¹ Each item had three response options: no problems, some problems, or serious problems. EQ-5D scoring profiles at successive measurements were converted into health utility scores using general population based tariffs of time trade-off ratings of health states.³² QALYs were calculated by taking the product sum of the health utility scores during follow-up and the interval lengths in years in-between successive measurements.

Health economic analysis methods

Analysis population

The CEA and CUA were done with the modified intention-to-treat population (see page 9) with references to the CONSORT-flow diagram in Figure SAP-1 and the baseline characteristics of the two RCT-subpopulations in Table EE1. Summary statistics for health utility scores at baseline were included in the manuscript text.

Cost-effectiveness threshold

The applied cost-effectiveness threshold for the sample size calculation was €120,000 as described and substantiated in the published study protocol.¹

Statistical decision rules

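### A randomised patient who does not start the allocated treatment has no explicit follow-up commitment, and one who starts neither therapy has no defined 12-month date

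*Protocol*

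**What the plan says.** **Time origin.** Protocol 7.3 lists the RCT visits after baseline, the later ones at "9 months, 12 months, 24 months and 36 months after start of the study treatment". Protocol 8.8 places the main clinical comparison "of the primary clinical outcome (PDQ-39) 12 months after the start of the study treatment". The SAP (Outcomes - randomized controlled trial) agrees: "The main clinical outcome was the change from baseline to 12 months after initiation of treatment in PDQ-39". The health economics analysis plan (HEAP) does not. Under Health outcomes it takes the "change in the PDQ-39 between baseline and 12 months after randomization" and also dates the EQ-5D from randomisation, while its section on perspective and time horizon counts 12 months from index surgery.

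**Sequence.** Under 7.3, randomisation follows the baseline assessment and the eligibility discussion. Treatment is to start within 3 months of baseline, so every patient spends some time randomised but untreated.

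**Who stays in follow-up.** Protocol 7.5: "In case a patient stops the study-treatment (CLI or DBS), the authors will strive to continue the follow-up assessments". Such a patient is not counted as a dropout. Nothing comparable is written for a patient who never begins.

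**Analysis principle.** Protocol 8.7: "Statistical analyses will be based on the intention-to-treat principle". Sections 7.5 and 12.5 repeat this, the latter for the economic evaluation.

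**What the SAP did.** Its synopsis of protocol development reports that several patients refused CLI at once and either took DBS or left the study. One reason given for making a modified ITT (mITT) population primary is that "for the patients for whom post-baseline data were not available, all these data would have had to be imputed". ITT becomes a sensitivity analysis that adds back "patients who immediately after randomization either had chosen not to accept the allocated treatment or had quitted participation in the study", with conformity, worst-case and best-case values where the outcome is missing.

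**The concern.** ITT needs an outcome from every randomised patient, including those who never begin what they were allocated. The protocol adopts ITT, but its visit clock starts at an event that some randomised patients never reach, and its retention rule is worded for patients who have already started.

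Refusal was foreseeable. Protocol 9.5 says that quicker access to DBS may motivate participation, and SAP Appendix I describes refusal of the allocated treatment as something that had been anticipated. No follow-up rule was written for it.

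The reported refusals concern CLI only, so the missing outcomes would fall in one arm. The ITT contrast would then depend on the value assigned to those patients, and the assigned value cannot show what happened to them.

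**Working it through.** **1. Which randomised patients have a 12-month date?**

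| Patient | Date for month 12 | Follow-up commitment in protocol |
|---|---|---|
| Starts allocated treatment and continues | Start of that treatment (7.3) | Scheduled visits (7.3) |
| Starts, then stops or crosses over | Start of that treatment (7.3) | Yes, worded for those who stop (7.5) |
| Refuses the allocated treatment, starts the other therapy | Can be read as start of the other therapy; not stated | None explicit |
| Starts neither therapy, still consents | None | None explicit |
| Withdraws from the study | Not applicable | Not applicable (7.4) |

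The gap is in the third and fourth rows. In the third, a date can be inferred. In the fourth, none exists under the protocol or the clinical SAP. The SAP's request to treating physicians about patients lost to follow-up does not fill it, because that too is dated from the start of the allocated treatment.

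**2. The plan's own sample size.** Inputs from Protocol 4.4: difference 0.2847 QALY, SD 0.35 QALY, cost SD €10,000, willingness to pay €120,000 per QALY, zero correlation, two-sided 0.05, power 80%, dropout 20%, PDQ-39 SD 15.

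- SD on the net-health-benefit scale = √(0.35² + (10,000/120,000)²) = 0.3598.
- The normal formula gives 26 per group; exact t-test power at 26 is 79.9%.
- 26 / 0.80 = 32.5, rounded up to 33 per group, 66 in total.
- With 26 per group and SD 15, the detectable PDQ-39 difference is 11.89, against 11.9 stated.

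The plan's figures reproduce and are not in dispute. The 33 per arm is used below.

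**3. Size of the dependence on assigned values.** The SAP says only that several patients refused. Assume that k of 33 CLI patients have no observed outcome and that their assigned values are wrong by d points on average, in one direction. The shift in the ITT CLI mean is (k/33) × d.

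| k | Share of CLI arm | d = 5 | d = 10 |
|---|---|---|---|
| 3 | 3/33 = 9% | 0.45 | 0.91 |
| 6 | 6/33 = 18% | 0.91 | 1.82 |

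The range is about 0.5 to 1.8 points. If the DBS arm has no such patients, the between-group difference moves by the same amount. For scale, the SAP takes 1.6 points as the minimal clinically important difference.

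**4. Loss of precision.** With 20% other dropout, a true difference of 11.9 and SD 15, power is 80.7% with no unmeasured non-starters, 78.0% with 4 and 76.3% with 6. That loss is modest; the main issue is the dependence on assigned values.

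**The case against.** A reader might infer that no never-starter has a 12-month visit, so that ITT must be imputed for all of them. The documents do not support this. Protocol 7.3 and 7.5 use study treatment for either therapy, so a CLI refuser who takes DBS has started a study treatment and can be dated from it. The SAP's as-treated analysis includes patients who switched immediately, classifies them by treatment at the 12-month visit where known, and imputes nothing. Its ITT section assigns values only where the outcome is missing, so using observed values first is already the plan.

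Nor do the documents show that the visit clock caused the missing data. The SAP links it to refusal and to leaving the study, and reports nobody who declined both therapies and stayed in. Patients who withdrew all consent would be missing under any wording.

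These objections narrow the point. What remains is that the as-treated section neither dates nor requires a visit for immediate switchers, and that a consenting patient who starts neither therapy has no date at all. The HEAP's randomisation origin does not close the gap: it conflicts with 7.3, 8.8 and the clinical SAP, and creates no visit. Timing is also a fair objection. The SAP is dated March 2022, so month-12 data missed earlier cannot be recovered.

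**Conclusion.** The point holds in a limited form. The protocol commits to ITT but gives no explicit follow-up commitment to a randomised patient who does not start the allocated treatment, and no defined 12-month date to one who starts neither therapy. Where such patients have no observed outcome, the ITT sensitivity analysis relies on assigned values, and the only refusals reported are of CLI.

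The shift of 0.5 to 1.8 points is illustrative. It rests on an assumed 3 to 6 patients, an assumed error of 5 to 10 points in one direction, and none of those patients being measured. As some refusers took DBS and may have been seen at 12 months, it is best read as an upper range for that count and error. It applies to the clinical ITT sensitivity analysis: the HEAP runs its analyses in the mITT population and lists no ITT version, although Protocol 12.5 plans the economic evaluation by ITT.

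The change is worth making because it affects what the trial collects and would reduce missing data in one arm.

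**What to change.** 1. In Protocol 7.3 and 7.5, state that a randomised patient who does not start the allocated treatment is not a dropout. Unless consent to follow-up is withdrawn, such a patient provides PDQ-39, EQ-5D and iMCQ/iPCQ by telephone or post at the planned times.
2. Date those assessments from an origin that exists for everyone, for example randomisation plus the planned interval to treatment start. Say explicitly how immediate switchers are dated.
3. Reconcile the time origin across Protocol 7.3 and 8.8, the SAP's main clinical outcome, and the HEAP's time horizon and health outcomes sections.
4. Report, by arm, how many patients never started the allocated treatment and how many of them have an observed 12-month outcome.

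The cost is protocol wording and a few remote assessments; the preference arms already use telephone assessments and postal forms. Month-12 data already missed cannot be recovered, but items 3 and 4 are still possible, and the SAP describes the 24- and 36-month follow-up as ongoing. On the downside, the month-12 clock would differ slightly between starters and never-starters, and patients who withdraw all consent would stay missing.
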